dexamethasone and dexamethasone 21-phosphate concentrations in the synovial fluid will be conducted based on the pharmacokinetic (PK) population.

Unless otherwise specified, all statistical assessments will be 1-sided and evaluated at the 5% level of significance.

All analyses, summaries, and listings will be performed using statistical analysis software (Version 9.2 or higher).

Further details regarding the definition of analysis variables and analysis methodology will be specified in a statistical analysis plan (SAP) to address all study objectives. The SAP will be developed and approved before database lock.

Analysis population:

The populations for analysis applied into this study are defined as follows:

- (1) Intent-to-treat population: all enrolled and randomized patients.
- (2) Safety population: All patients who receive any dose of study drug administration will be included in the safety population.
- (3) Modified Intent-to-treat population: The mITT population indicates all enrolled patients who receive one complete dose of study drug administration and have at least one complete efficacy evaluation after study drug dosing.
- (4) Per-protocol population: The PP population is a subset of mITT population fulfilling evaluable criteria without any major protocol deviation and has evaluation at baseline, Week 12 and at least 2 other evaluation within 12 weeks.
- (5) Pharmacokinetics population: All ITT patients who receive any dose of study drug, and those who consented for synovial fluid collection from the study knee at the end of study (EOS)/early termination (ET) visit.

Efficacy analysis:

All efficacy analyses will be conducted for the mITT and PP populations as well as ITT population.

For the primary efficacy analysis, the overall change from baseline in WOMAC pain subscale over 12 weeks will be analyzed using a mixed-effects model for repeated measures (MMRM) with restricted maximum likelihood estimation. The model will include factors of treatment, visit (as a categorical variable), baseline value of the WOMAC pain subscale score as fixed factors, site as random factor, and treatment-by-visit as interaction terms. This methodology will be used to compare treatment groups for change from baseline through Week 12. The model estimates by treatment group, contrast estimates for between-group (pairwise) comparisons, standard errors, 90% CIs, and p-values will be presented.

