An MMRM model as described for primary efficacy analysis will be used to analyze the overall change from baseline in WOMAC pain / function subscale and VAS over 12, 16, 20 and 24 weeks as well as the change from baseline in WOMAC pain / function subscale and VAS at each scheduled visit.

Analysis of covariance (ANCOVA) is to be used for secondary efficacy endpoints measured in continuous scale, including treatment group, and the baseline value of that endpoint and the study sites as covariate if appropriate. Within each treatment group, the total consumption of acetaminophen, changes from baseline in patient-rated VAS, WOMAC pain subscale, WOMAC function subscale, and EQ-5D at scheduled time points, and AUEC of VAS/WOMAC pain subscale will be summarized using descriptive statistic and estimated using the least squares mean. The 2-sided 90% confidence interval for LSM will be reported for each treatment arm.

The frequency and percentage will be used to summarize patients achieving the response criteria at scheduled time points and patients achieving the durable response criteria and will be presented by treatment group. Treatment comparisons of each TLC599 dose treatment with placebo will be made using a logistic regression analysis with treatment group, study site, and the baseline value of that endpoint as covariate in the model.

Explorative univariate models will be used to identify the possible prognostic factors associated with

WOMAC pain subscale and VAS, e.g. age, gender, race, unilateral or bilateral knee pain, and baseline severity by VAS or pain score and Kellgren-Lawrence grades. The subgroup analysis will be performed according to the results of regression model.

Safety analysis:

The assessment of safety will be based mainly on the frequency of adverse events (AEs), which includes all serious AEs (SAEs) and AEs, clinical laboratory data, vital signs, physical examination, electrocardiogram (ECG) result, articular cartilage assessment by MRI, and other safety findings.

All safety variables will be summarized using descriptive statistic based on the safety population. No inferential statistics are planned.

Pharmacokinetics analysis:

The concentrations of dexamethasone and dexamethasone 21-phosphate in the synovial fluid of the study knee at EOS will be summarized by treatment group using descriptive statistics.

Schedule of Events

Visit	Screening	1(Baseline)	2	3	4	5	6	7	8	EOS/E T

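### The secondary MMRMs for WOMAC function and VAS, read literally, adjust for baseline WOMAC pain and not for their own baseline, at a modest cost in precision for function

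*Combined protocol and SAP*

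**What the plan says.** All of this is in the synopsis, Statistical methods, Efficacy analysis.

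- **Primary MMRM.** After treatment and visit, the model has "baseline value of the WOMAC pain subscale score as fixed factors, site as random factor, and treatment-by-visit as interaction terms". The covariate is named as a particular scale, not as the baseline of whatever is being analysed.
- **Secondary MMRM.** The plan says: "An MMRM model as described for primary efficacy analysis will be used to analyze the overall change from baseline". The scales and horizons to which this applies are given as "WOMAC pain / function subscale and VAS over 12, 16, 20 and 24 weeks"; by-visit changes are analysed in the same way. No change of covariate is stated.
- **ANCOVA.** Continuous secondary endpoints are adjusted for treatment group and "the baseline value of that endpoint and the study sites as covariate if appropriate". The quantities then listed for least squares means include "changes from baseline in patient-rated VAS, WOMAC pain subscale, WOMAC function subscale, and EQ-5D at scheduled time points".
- **Responder analyses.** These use a "logistic regression analysis with treatment group, study site, and the baseline value of that endpoint as covariate in the model".

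The General statistical considerations leave further detail to a SAP, to be approved before database lock.

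**The concern.** The generic own-baseline wording appears in the ANCOVA and logistic paragraphs but not in the MMRM paragraph. A programmer who follows the text would put baseline WOMAC pain into the function and VAS models. A change score contains its own baseline. If that baseline is not in the model, part of its variation stays in the residual, and the treatment contrast is less precise than the collected data allow.

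Two things are at stake. The first is precision for function in a trial that expects about 20 completers per arm. The second is clarity: the by-visit changes in function and VAS would be estimated by two models with different baseline covariates, and the plan does not say which one leads.

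**Working it through.** **The plan's own figure.** 20 completers and 15% drop-out give 20/(1 − 0.15) = 23.53, rounded up to 24 per arm, and 3 × 24 = 72. This reproduces, and it does not depend on the covariate.

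**Which model covers which quantity (function and VAS)**

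| Quantity | MMRM, read literally | ANCOVA |
|---|---|---|
| Change at each visit (Secondary Endpoint 1) | baseline pain | own baseline |
| Overall change through Weeks 12, 16, 20, 24 (Secondary Endpoint 2) | baseline pain | not named |

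**Size of the loss.** The documents give no correlations, SDs or effect size, so every input below is an assumption.

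- Y is the follow-up score with SD 1, B its own baseline, and P baseline pain.
- ρ = corr(Y, B), r = corr(B, P), and k = SD(B)/SD(Y).
- corr(Y, P) = ρr, meaning that baseline pain predicts later function only through baseline function.

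Residual variance of the change Y − B:

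- adjusted for own baseline: 1 − ρ²
- adjusted for baseline pain: 1 + k² − 2ρk − r²(ρ − k)² = (1 − ρ²) + (ρ − k)²(1 − r²)

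The variance ratio is R = 1 + (ρ − k)²(1 − r²)/(1 − ρ²). The SE ratio is √R, and the equivalent share of patients lost is 1 − 1/R.

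| k | ρ | r | R | SE ratio | Patients lost | 20 completers worth |
|---|---|---|---|---|---|---|
| 1 | 0.3 | 0.5 | 1 + 0.49 × 0.75/0.91 = 1.404 | 1.18 | 29% | 14.2 |
| 1 | 0.5 | 0.7 | 1 + 0.25 × 0.51/0.75 = 1.170 | 1.08 | 15% | 17.1 |
| 1 | 0.6 | 0.8 | 1 + 0.16 × 0.36/0.64 = 1.090 | 1.04 | 8% | 18.3 |
| 0.7 | 0.3 | 0.5 | 1 + 0.16 × 0.75/0.91 = 1.132 | 1.06 | 12% | 17.7 |
| 0.7 | 0.6 | 0.8 | 1 + 0.01 × 0.36/0.64 = 1.006 | 1.00 | 1% | 19.9 |

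The loss vanishes when ρ = k.

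**VAS.** Inclusion criterion 4 restricts baseline VAS to 5.0 to 9.0, so k may well be below 1. At k = 0.5 the SE ratio over the same correlations is 1.00 to 1.02. A simulation with baseline VAS truncated to that range gave 1.01 to 1.04.

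**Mean over visits.** The table is for one visit. For the mean of four visits, also assume equal SDs and a between-visit correlation of 0.7. The variance of the mean is (1 + 3 × 0.7)/4 = 0.775, which replaces the 1 in 1 − ρ². The ratios are then √(1 + 0.3675/0.685) = 1.24 and √(1 + 0.0576/0.415) = 1.07 at the two extreme corners of the range. A simulation with 24 per arm, three arms and 4,000 repetitions agrees: 1.18 at (ρ, r) = (0.4, 0.6) and 1.08 at (0.6, 0.8).

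**Bias.** In that simulation the true contrast was zero. The average estimate stayed within 0.01 SD of zero under either covariate.

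**Power, for illustration.** The plan states that "all statistical assessments will be 1-sided and evaluated at the 5% level of significance". With 20 per arm and a difference of 0.8 residual SD, own-baseline power is 81%. It becomes 78%, 75% and 72% at variance ratios of 1.10, 1.20 and 1.30.

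**The case against.** The strongest reply is that the primary model is being used as a template. The secondary sentence already changes the response and the time horizon, so it is natural to suppose that the baseline changes too, and the ANCOVA and logistic paragraphs suggest that intent. This stands as a plausible reading. It is not written, though, and the only covariate named is "baseline value of the WOMAC pain subscale score as fixed factors".

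Further detail is also deferred to a SAP. If a SAP specifies the matching baseline, only consistency with the synopsis remains to be checked.

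Three stronger readings are tempting and are not supported:

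- **That the plan never adjusts function or VAS for its own baseline.** The ANCOVA names the by-visit changes and uses the endpoint's own baseline, if appropriate. Its opening words, on continuous secondary endpoints in general, might be stretched to the overall changes, but these are named only under the MMRM.
- **That the contrasts are biased.** Regression to the mean acts on all randomized arms alike. A chance imbalance in own baseline has an SE of √(2/24) = 0.29 SD. The part that reaches the contrast has an SE of about 0.29 × √(1 − r²) × (1 − ρ), or 0.07 to 0.18 SD over the assumed range with k = 1. That is the source of the wider interval, not a second harm.
- **That VAS suffers materially, or that the primary analysis or sample size is affected.** The VAS loss is negligible. The primary endpoint is WOMAC pain, for which the named covariate is the right one, and 24 per arm stands.

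**Conclusion.** The MMRM baseline covariate for function and VAS is, as written, that of another scale, and this is inconsistent with the plan's other secondary models. The overall changes through Weeks 12 to 24 have no explicitly named own-baseline analysis.

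For function at a single visit, the SE is about 1.04 to 1.18 times that of the own-baseline model, assuming ρ of 0.3 to 0.6, r of 0.5 to 0.8 and equal SDs. It is about 1.00 to 1.06 times if the baseline SD is 0.7 of the follow-up SD. A mean over visits can lose somewhat more, under the further assumption shown.

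Severity is minor: these are secondary endpoints of a study that calls itself exploratory and has no formal sample size calculation. The point is still worth acting on, because own-baseline adjustment gains precision at no cost.

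**What to change.** In the SAP, before database lock, state that each secondary MMRM has the primary model's structure with the baseline value of the scale being analysed (function for function, VAS for VAS) in place of baseline WOMAC pain. Baseline pain may stay as an additional term. State also whether the MMRM or the ANCOVA is the main analysis of the by-visit changes in function and VAS, with the other as supportive.

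The cost is two sentences. The Schedule of Events already collects WOMAC and VAS at Visit 1. The primary analysis and the 24 per arm (72 in total) do not change.

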- (4) Area under the effect curve of the WOMAC pain subscale from baseline to Week 12, 16, 20 and 24.
- (5) Proportion of responders by a decrease of > 30% or > 50% in patient-rated VAS from baseline to Weeks 1, 4, 8, 12, 16, 20, and 24.
- (6) Proportion of responders by a decrease of > 30% or > 50% in WOMAC pain subscale from baseline to Weeks 1, 4, 8, 12, 16, 20, and 24.
- (7) Proportions of durable responders with persistent response since Week 1 till Weeks 12, 16, 20, and 24, respectively, by pain relief > 30% in VAS.
- (8) Proportions of durable responders with persistent response since Week 1 till Weeks 12, 16, 20, and 24, respectively, by pain relief > 30% in WOMAC pain subscales.
- (9) Proportions of durable responders with persistent response since Week 1 till Weeks 12, 16, 20, and 24, respectively, by outcome measured in rheumatology- Osteoarthritis Research Society International set of responder criteria.
- (10) Change from baseline to Weeks 1, 4, 8, 12, 16, 20, and 24 in EuroQol-5 Dimension questionnaire.
- (11) Total consumption of acetaminophen at Weeks 1, 4, 8, 12, 16, 20, and 24.
- (12) Safety and tolerability.

Pharmacokinetic Endpoints:

The concentrations of dexamethasone and dexamethasone 21-phosphate in synovial fluid of the study knee joint at end of study or early termination.

Statistical methods:

Sample size calculation:

This is an exploratory study and there is no formal sample size evaluation. It is expected to have approximately 20 patients in each study groups completing 24-week follow-up period after study drug administration. Given a drop-out rate of 15%, approximately 24 patients in each study group will be enrolled and a total of approximately 72 patients will be randomly assigned.

General statistical considerations:

All efficacy and safety variables will be summarized using descriptive statistics. Continuous variables will be presented as number of observations, mean, standard deviation, median and range; while categorical variables will be presented as number of observations, count, and percentage in frequency table.

In this study, safety population is used for any safety analysis. The intent-to-treat (ITT), modified Intent-to-treat (mITT) and per-protocol (PP) populations will be used in analysis of efficacy variables, but the major efficacy conclusion will be based on the results obtained from mITT population. The analysis of

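### Does the plan leave open whether MMRM or ANCOVA governs by-visit change in VAS, WOMAC pain and WOMAC function?

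*Combined protocol and SAP*

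**What the plan says.** All the relevant text is in the synopsis, under Statistical methods.

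- **Primary model.** Change in WOMAC pain through Week 12 is analysed by MMRM with "site as random factor, and treatment-by-visit as interaction terms". Estimates by arm are to be shown, and "contrast estimates for between-group (pairwise) comparisons, standard errors, 90% CIs, and p-values will be presented".
- **Secondary use of the MMRM.** The same model specification is carried to overall change over 12, 16, 20 and 24 weeks, "as well as the change from baseline in WOMAC pain / function subscale and VAS at each scheduled visit".
- **ANCOVA.** The following paragraph begins: "Analysis of covariance (ANCOVA) is to be used for secondary efficacy endpoints measured in continuous scale". Its terms are treatment, the baseline value and "the study sites as covariate if appropriate".
- **LS means.** The same paragraph says that, within each arm, acetaminophen use, "changes from baseline in patient-rated VAS, WOMAC pain subscale, WOMAC function subscale, and EQ-5D at scheduled time points", and the AUEC endpoints are summarised descriptively and estimated by LS means. It adds: "The 2-sided 90% confidence interval for LSM will be reported for each treatment arm".
- **Population and timing.** On populations, "the major efficacy conclusion will be based on the results obtained from mITT population". General statistical considerations leaves further detail on methods to an SAP that is to be approved before database lock.

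**The concern.** By-visit change in the three measures is the first secondary endpoint, so it is a continuous secondary endpoint and falls within the ANCOVA sentence as written. The preceding paragraph has already given it to the MMRM. No sentence ranks the two models or limits ANCOVA to what is left over.

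The models are not interchangeable. The MMRM uses every visit and treats site as random. The ANCOVA may or may not carry a site term, and the text does not say what it does with missing visits. An analyst could therefore defend MMRM, ANCOVA with site or ANCOVA without site for the same table.

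In a dose-finding trial the by-visit results out to Week 24 show how long each dose lasts. Two versions with no stated priority would allow the more attractive one to be put forward after the data are seen. If an ANCOVA used only patients still attending, late means could also look too good when poor responders leave.

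**Working it through.** **Inputs from the documents.** About 20 completers per arm, 15% dropout, 3 arms, 8 to 13 sites, seven scheduled weeks for the by-visit endpoint, one-sided 5% tests and two-sided 90% intervals.

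**The plan's own figures.**
- Enrolment: 20 / (1 - 0.15) = 23.5, rounded up to 24 per arm; 24 x 3 = 72. This agrees with the plan.
- A one-sided 5% test and a two-sided 90% interval share the critical value 1.645, so the two conventions are consistent.

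**Extent of the overlap.**
- Per-arm LS means: 3 measures x 7 visits x 3 arms = 63. Counting the Day 3 assessment in the Schedule of Events as well gives 3 x 8 x 3 = 72, but the endpoint list names only the seven weeks.
- Dose-placebo contrasts, if anyone took them from both models: 3 x 7 x 2 = 42.
- Site as a fixed term: 8 - 1 = 7 to 13 - 1 = 12 degrees of freedom, with 72 x 0.85 = 61.2 patients expected at Week 24.

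**The two paragraphs side by side.**

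| | MMRM text | ANCOVA text |
|---|---|---|
| Endpoints | Names WOMAC pain, WOMAC function and VAS by visit | Continuous secondary endpoints in general |
| Site | Random | Covariate, conditionally |
| Promised output | Arm estimates, pairwise contrasts, standard errors, 90% CIs, p-values | LS mean and 90% CI per arm |
| Model named for the LS means | Yes | Not in the sentence that re-lists the three measures |

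The MMRM itself yields arm-level LS means with 90% CIs at each visit, so the re-listing can be satisfied without an ANCOVA of these measures. Read that way, ANCOVA is left with AUEC, EQ-5D and acetaminophen use, none of which is given to the MMRM.

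**How far apart the versions could be (simulation; only arm size and dropout rate come from the documents).** Assumed: 3 arms of 24, 10 sites with variance 0.05, 8 post-baseline visits, 15% dropout in each arm, and within-patient correlation of 0.6 exchangeable, 0.8 AR(1) or a mixture. The MMRM was idealised as generalised least squares with known covariances. The ANCOVA used only patients seen at Week 24. There were 400 trials per setting.

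*Dropout unrelated to response.* Neither version is biased. The SD of the difference between the two Week 24 per-arm LS means, in outcome SD units, was:

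| | Mixture | AR(1) | Exchangeable |
|---|---|---|---|
| ANCOVA without site | 0.086 | 0.103 | 0.051 |
| ANCOVA with site | 0.116 | 0.134 | 0.084 |

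The 90% CI half-width was 0.31 to 0.40. Interval width relative to the MMRM was 0.96 to 0.98 without site and 1.02 to 1.06 with site.

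*Poor responders more likely to leave, equally in each arm (large-sample runs).* Bias of the ANCOVA per-arm mean:

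| Dropout driven by | LS mean at baseline mean of all patients | LS mean at baseline mean of patients still seen |
|---|---|---|
| Last change from baseline | 0.020 to 0.124 | 0.032 to 0.221 |
| Last score itself | 0.021 to 0.104 | at most 0.015 |

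With dropout driven by last change, the contrast bias stayed within 0.01. At trial size in that setting the MMRM per-arm bias was at most 0.034, with Monte Carlo error of about 0.008.

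*If ANCOVA contrasts were also tested.* A simpler two-arm simulation (24 per arm, random dropout, correlation 0.5 or 0.7, site omitted, 1,000 trials per scenario) put MMRM and ANCOVA on opposite sides of the one-sided 5% line at Week 24 in about 2% to 4% of trials with no effect and 8% to 15% with a 0.5 SD effect.

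**The case for a change.** The strongest case for a change is that the rule that the specific prevails over the general is not written down, and the ANCOVA paragraph is itself specific: it names the three measures again, immediately after setting out the ANCOVA terms and alongside endpoints that have no MMRM. An ANCOVA with a treatment term also produces contrasts whether or not they are promised, and the 8% to 15% disagreement shows that the choice can matter for a single visit. One or two sentences would settle it.

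Part of this stands. The limiting word is missing, and 63 LS means could be produced twice. Three things weaken the rest.

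- The disagreement rates presuppose ANCOVA tests that the plan does not promise for these measures. For them it promises contrasts and p-values only from the MMRM.
- The per-arm bias rests on an assumed dropout mechanism and an assumed ANCOVA of observed cases. Depending on the mechanism and on the baseline value at which the LS mean is evaluated, it ranges from about 0 to 0.22 SD, so no single figure can be charged to the plan.
- The conditional site term is a reasonable allowance for about 72 patients over 8 to 13 sites (72 / 13 = 5.5 to 72 / 8 = 9 per site). Asking for a flat yes or no is a preference, and it would also bind AUEC, EQ-5D and acetaminophen use, where there is no overlap.

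**Conclusion.** The wording overlaps, but this is a gap that analysts fill sensibly, and no change is needed. The specific MMRM assignment governs by-visit VAS and WOMAC change, ANCOVA serves the continuous endpoints the MMRM does not cover, and any ANCOVA of the three measures is supportive. Ranking two methods that the plan already states is ordinary SAP work, and the SAP is due before database lock.

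What could be duplicated is at most 63 per-arm LS means in the mITT population. The primary analysis is untouched, and the study is declared exploratory with no formal sample size calculation. With dropout unrelated to response, the versions differ by an SD of 0.05 to 0.13, well inside a 90% half-width of 0.31 to 0.40. With response-linked dropout equal across arms, a per-arm ANCOVA mean could be off by about 0 to 0.22 SD, but the dose-placebo contrast is not materially biased.

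These sizes depend on the assumed correlations, site variance, dropout mechanism and observed-case ANCOVA, none of which the documents give. Dropout that differs between arms could bias an observed-case ANCOVA contrast, but the plan does not promise such a contrast for these measures.

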- At Visit 1, some local sites may have facility constraint for study drug preparation. Randomization, VAS, WOMAC, and EQ-5D questionnaires should be performed at the same day. Study drug administration is allowed to be performed at the same day as randomization or one day after randomization. The day of study drug administration is defined as Day 0.
- For patient with excessive synovial effusion, it is accepted to aspirate the excessive synovial fluid during study drug administration procedure. However, the characteristic and amount of the aspirated fluid should be recorded. The aspirated fluid can be sent for laboratory examination if there is any concern of infection, intra-articular bleeding or the OA diagnosis is questionable.
- For the articular cartilage evaluation of the knees, all subjects should have MRI examination conducted for MOAKS grading during the screening period or prior to randomization, and at the end of study/early termination. MRI images will be performed for both knees.
- MRI examination can be performed within 21 days prior to EOS/ET visit.

10. Use of acetaminophen will be recorded on diary card.
 11. Synovial fluid from the study knee will be collected after completion of efficacy evaluation (VAS, WOMAC and EQ-5D) at EOS or within 3 days after ET visit, only if the subject has provided written informed consent for this procedure. In addition, it will only be aspired if appropriate synovial fluid volume in the study knee is ensured by local ultrasound examination and/or at the investigator's discretion prior to the aspiration.
- Abbreviations: AE=adverse event; BP=blood pressure; ECG=electrocardiogram; EOS=end of study; EQ-5D=EuroQol-5 Dimension; ET=early termination; HbA1c=glycosylated hemoglobin; HR=heart rate; INR= international normalized ratio; MOAKS=MRI Osteoarthritis Knee Score; MRI=magnetic resonance imaging; PA=posterior-anterior; PT=prothrombin time; aPTT=partial thromboplastin time; RR=respiratory rate; SAE=serious adverse event; VAS=visual analogue score; WOMAC=Western Ontario McMaster Universities.

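### EQ-5D is collected at every WOMAC and VAS visit but is assigned to ANCOVA by time point rather than the MMRM, which leaves its late estimates open to modest bias if dropout follows response

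*Combined protocol and SAP*

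**What the plan says.** Secondary endpoint 10 in the synopsis is "Change from baseline to Weeks 1, 4, 8, 12, 16, 20, and 24 in EuroQol-5 Dimension questionnaire". In the Schedule of Events the EQ-5D row is identical to the VAS and WOMAC rows: baseline, Day 3, Weeks 1, 4, 8, 12, 16 and 20, and the shared EOS/ET visit at Week 24. A footnote on Visit 1 adds that "Randomization, VAS, WOMAC, and EQ-5D questionnaires should be performed at the same day".

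Under Efficacy analysis, the primary MMRM is extended to the overall changes in WOMAC pain, WOMAC function and VAS, "as well as the change from baseline in WOMAC pain / function subscale and VAS at each scheduled visit". EQ-5D is not named there. The next paragraph says "Analysis of covariance (ANCOVA) is to be used for secondary efficacy endpoints measured in continuous scale", adjusting for treatment, baseline and, if appropriate, site. Its list of quantities to be estimated within each arm covers acetaminophen use, AUEC, the changes in VAS and WOMAC pain, and "WOMAC function subscale, and EQ-5D at scheduled time points". It closes with "The 2-sided 90% confidence interval for LSM will be reported for each treatment arm".

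Three other statements bear on the point:
- The sample size section expects about 20 completers per arm from 24 enrolled, at 15% dropout.
- The main efficacy population (mITT) requires a full dose and only one complete post-dose efficacy assessment.
- Further method detail is left to a SAP to be approved before database lock. No missing-data rule for EQ-5D appears in the synopsis or the schedule.

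**The concern.** An ANCOVA at one time point has no visit term and no within-patient covariance. Unless missing values are filled in, it uses only patients with a value at that visit. A patient who leaves at Week 8 stays in the mITT population and has several EQ-5D scores on file, yet contributes nothing to the Week 24 estimate. The MMRM planned for pain and function would use those scores.

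If patients with a poor response leave more often, those who remain look better than the arm as a whole. The per-arm means, which the plan does promise for EQ-5D, are then too favourable. The dose-placebo difference can also be wrong if the selection differs between arms. An MMRM removes this bias when dropout depends only on observed earlier scores, baseline and arm. The documents give no reason for treating EQ-5D differently.

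**Working it through.** **1. The plan's own figure.** From the sample size section: 20 completers per arm and 15% dropout. 20 / (1 − 0.15) = 23.5, rounded up to 24; 3 × 24 = 72. The stated enrolment reproduces.

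**2. Patients behind a Week 24 ANCOVA.** 20 / 24 = 83% of each arm. Relative to complete data, the standard error grows by √(24/20) = 1.095, about 9.5%. This is the cost of losing patients; step 4 shows how little of it a different model recovers.

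**3. Bias when dropout follows response.** The documents give no EQ-5D variance, correlation or dropout mechanism, so all of these are assumed. Units are between-patient SDs of the score at a visit.

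Set A: 24 per arm, 8 post-baseline visits, between-visit correlation 0.6 to 0.8, true Week 24 effect 0.50 SD, response-driven dropout of about 18% on placebo and 10% on active, 2,000 trials per scenario. The mean ANCOVA estimates were 0.469, 0.456 and 0.459, that is 0.031, 0.044 and 0.041 SD below 0.50, or 6 to 9%. The repeated-measures fit gave 0.508, 0.503 and 0.507.

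Set B: 3 arms of 24, 8 post-baseline visits, true effect 0.50 SD, placebo improvement 0.50 SD, overall dropout 15%, and a logistic dropout hazard on the last observed score (slope 1.5 per SD), 2,000 trials per scenario. ANCOVA results at Week 24:

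| Correlation | Poor responders leave in | Dropout, placebo / active | Bias, placebo mean | Bias, difference | SE of difference | Bias / SE |
|---|---|---|---|---|---|---|
| Exchangeable 0.5 | all arms | 21% / 12% | +0.071 | −0.032 | 0.273 | 0.12 |
| Exchangeable 0.7 | all arms | 21% / 12% | +0.067 | −0.033 | 0.226 | 0.15 |
| AR(1) 0.8 | all arms | 21% / 12% | +0.101 | −0.044 | 0.316 | 0.14 |
| AR(1) 0.9 | all arms | 21% / 12% | +0.103 | −0.036 | 0.282 | 0.13 |
| Exchangeable 0.5 | placebo only | 23% / 11% | +0.083 | −0.080 | 0.276 | 0.29 |
| Exchangeable 0.7 | placebo only | 23% / 11% | +0.060 | −0.057 | 0.237 | 0.24 |
| AR(1) 0.8 | placebo only | 23% / 11% | +0.118 | −0.115 | 0.307 | 0.37 |
| AR(1) 0.9 | placebo only | 22% / 12% | +0.112 | −0.106 | 0.288 | 0.37 |

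The repeated-measures fit stayed within 0.01 SD of the truth in every row. Simulation error on a mean difference is about 0.226/√2000 = 0.005 to 0.316/√2000 = 0.007. With dropout unrelated to response, ANCOVA bias was also within 0.01 SD. At an assumed 30% dropout (exchangeable 0.7), the ANCOVA bias was +0.11 to +0.13 in the placebo mean and −0.05 to −0.11 in the difference.

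**4. Precision.** With dropout unrelated to response, the SE of the difference (ANCOVA, then repeated measures) was as follows:
- Set A: 0.273 and 0.266, 0.290 and 0.277, 0.262 and 0.251. The reductions are 1 − 0.266/0.273 = 3%, 4% and 4%.
- Set B: 0.275 and 0.273, 0.228 and 0.226, 0.315 and 0.310, 0.287 and 0.278. The reductions run from 1% to 3%.

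Under response-driven dropout in set B the two SEs differ by less than 2%, in either direction.

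**5. Limits.** Both sets use an unstructured likelihood fit with monotone dropout, and set B has no site effect. The plan's model is REML with random site, and its covariance structure is not stated in the synopsis.

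**The case against.** A reader might infer that the plan states an observed-cases analysis and discards leavers' data. It does not say so. That is the natural reading of an ANCOVA at a time point with no imputation rule, but the SAP is still to come and the ITT analysis of all randomized patients will need some rule. EQ-5D is also marked in the EOS/ET column, so leavers who attend an early-termination visit supply a last value. Whether it counts as Week 24 is not stated. This part of the objection stands and limits how firmly the consequence can be put.

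A reader might also infer that EQ-5D alone is singled out for ANCOVA, on a different missing-data assumption from pain and function. The ANCOVA paragraph lists the VAS and WOMAC changes as well, so those have two methods and EQ-5D has one. The accurate statement is that EQ-5D is the only one of the three instruments with no MMRM, and that the two paragraphs overlap.

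It can further be said that the plan clearly promises only per-arm means with 90% intervals for EQ-5D, not dose-placebo contrasts. That is fair. It makes the arm-level bias the more relevant figure, and that bias does not cancel between arms.

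Finally, it goes too far to say that the ANCOVA difference is unbiased only when leaving is unrelated to earlier EQ-5D. With no treatment effect and the same dropout mechanism in each arm, the selection is the same and the difference is unbiased.

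None of this answers the main point: a method is already named for EQ-5D, and a better one is already planned for data collected at the same visits.

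**Conclusion.** The point stands at low severity. If the ANCOVA is run on observed values and dropout follows earlier response, the Week 24 placebo mean is biased by about 0.06 to 0.12 SD. The dose-placebo difference is then biased by about 0.03 to 0.12 SD, 0.12 to 0.37 of its standard error in set B. The upper end of the range for the difference needs response-driven dropout in placebo only. The direction was toward a smaller effect in every scenario run, but other mechanisms could reverse it. All of these sizes rest on assumed correlations, effect and dropout mechanism.

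If dropout is unrelated to response there is no bias. Precision is not a strong reason for the change: the MMRM gains at most 3 to 4% of SE, and most of the 9.5% loss from 24 to 20 patients remains under either method. A conclusion that the EQ-5D results would be seriously misleading is not supported. This is one secondary endpoint in a study described as exploratory, and the primary analysis is unaffected.

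**What to change.** In the synopsis's Efficacy analysis section, and in the SAP that follows it:

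- Add EQ-5D to the secondary MMRM sentence, with its own baseline, treatment, visit, treatment-by-visit and random site. Report per-arm estimates and dose-placebo contrasts at each visit.
- Keep ANCOVA for endpoints with one value per patient, such as AUEC.
- Take the VAS and WOMAC changes out of the ANCOVA paragraph, so that each endpoint has one stated method.
- State how an EQ-5D value from an early-termination visit is assigned to a scheduled visit.

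The cost is SAP wording and one more run of a model already planned. No new data are needed.
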